8.4. Safety Monitoring

The TRACON Clinical Team will monitor safety throughout the study via the following activities:

- Surveillance for SAEs according to regulatory guidelines
- Routine monitoring of non-serious adverse experiences as they are recorded in the case report forms and the source documents at study sites
- A formally chartered TRACON in-house Safety Review Team that includes, among other staff, two physicians
- Periodic teleconferences with the Principal Investigators to share experiences and ensure communication
- Toxicity information that may affect the treatment of patients on this study will be promptly communicated in writing to all participating clinical sites and institutions participating in this clinical trial.
- In addition a Data Monitoring Committee (DMC) will review the data from the trial. The DMC will periodically review the progress of the study and accumulating safety and efficacy data. Following each review, the DMC will recommend to the Sponsor (TRACON Pharma) whether to continue the trial unchanged, modify the conduct of the

study, or terminate the study early. The TRACON Safety review Team will then determine whether to accept or modify the DMC recommendations and will communicate with study sites and regulators as appropriate. The DMC will be comprised of 3 voting members external to the Sponsor, including a clinician specializing in the treatment of renal cell cancer, a clinician with broader specialty in oncology clinical studies, and a biostatistician with expertise in the design, analysis, and interpretation of oncology clinical studies.

8.5. Steering Committee

An external steering committee comprised of renal cell cancer experts will assist with study design and will review study amendments as needed.

9. OTHER ASSESSMENTS

9.1. Other Laboratory Assessments

9.1.1. Pharmacokinetics (Phase 1b and Phase 2)

Samples will be sent to third party laboratory. See separate laboratory manual for specific collection, storage and shipping information.

9.1.1.1. TRC105 Trough Concentration (Phase 1b and Phase 2 Arm B)

A 5 mL blood sample will be collected immediately prior to dosing with TRC105 on the days indicated within the Schedule of Assessments. Samples will be separated and stored at approximately -70 °C for shipment to third party laboratory. See separate laboratory guide for further collection and shipment information. For patients receiving axitinib and TRC105 in the study, population PK analysis will be performed for TRC105 in accordance with the FDA guidance on Population Pharmacokinetics (February 1999) and EMA Guideline on reporting the results of population pharmacokinetic analyses (June 2007). The serum concentration data set from this study will be pooled with data sets from additional TRC105 Phase 2 studies in other oncology populations. Population PK analyses will involve mixed effects modelling performed using appropriate software.

TRC105 Peak Concentration (Phase 1b)

A 5 mL blood sample will be collected within 10 minutes following each TRC105 infusion on the days indicated within the Schedule of Assessments. Samples will be separated and stored at approximately -70 °C for shipment to third party laboratory. See separate laboratory guide for further collection and shipment information.

9.1.1.2. Axitinib Trough Concentration (Phase 2)

A 5 mL blood sample will be collected immediately prior to dosing with TRC105 and axitinib on the days indicated within the Schedule of Assessments. Samples will be separated and stored at approximately -70 °C for shipment to third party laboratory. See separate laboratory guide for further collection and shipment information.

9.1.2. TRC105 Immunogenicity

Samples will be sent to a third party laboratory for storage. See separate laboratory manual for specific collection, storage and shipping information.

Anti-Product Antibody (APA) concentrations will be measured using validated ELISA methods at the timepoints specified in the Schedule of Assessments in all patients. APA concentrations will be evaluated in the context of pharmacokinetic parameters and AE profiles. Samples will be separated and stored at approximately -70 °C for shipment to a third party laboratory. See separate laboratory guide for further collection and shipment information.

9.1.3. Protein Biomarkers

One 10 mL purple top (K₂EDTA) tube of blood will be collected on the days indicated within the Schedule of Assessments. Samples will be stored at approximately -70 °C and shipped to a third party laboratory for storage until the time of analysis. Duke University Medical Center will analyze plasma for several biomarkers including but not limited to VEGF, VEGF-R2, PIGF and sCD105 (Phase 1 Biomarker Laboratory, Duke University Medical Center, [name]). Please see the separate laboratory guide for further collection and shipment information.

9.1.4. Archival Tumor Specimens

Archival specimens (formalin-fixed, paraffin-embedded) of the primary cancer and/or metastatic cancer specimen for each study participant will be obtained, if they are available. It is preferable that the entire paraffin block be submitted, but if this is not feasible, then at least 20 unstained slides are requested for immunohistochemical analysis (sections of ~ 5 microns are preferred). Samples will be stored at room temperature and shipped to third party laboratory for storage until the time of analysis. See separate laboratory guide for further collection and shipment information.

10. STATISTICS

10.1. Phase 1b

10.1.1. Statistical Design/Sample Size

The number of patients to be enrolled in this study will depend upon the observed safety profile, which will determine the number of patients per dose level and the number of dose escalations. It is anticipated that up to 18 patients will be enrolled in this study.

The probability of escalation to the next higher dose for each underlying true DLT rate is shown in Table 22. For example, at a dose level with a true DLT rate of 5%, there is a greater than 95% probability of escalating. Conversely, for a dose level with a true DLT rate of 70%, the probability of escalating is < 5%.

Table 22: Probability of Escalation to the Next Dose for Each True Underlying DLT Rate at a Dose Level

True Underlying DLT Rate	5%	10%	20%	30%	40%	50%	60%	70%	80%	90%
Probability of Escalating Dose	0.97	0.91	0.71	0.49	0.31	0.17	0.08	0.03	0.01	0.001

Expanded Cohort 1:

The probability of failing to observe DLT in a sample size of 3 patients given various true underlying DLT rates is shown in Table 23. For example, with 3 patients, the probability of failing to observe DLT occurring at least 50% of the time is less than 15%.

Table 23: Probability of Failing to Observe True Underlying DLT Rate at a Dose Level

True Underlying DLT Rate	5%	10%	20%	30%	40%	50%	60%	70%	80%	90%
Probability of Failing to Observe Toxicity if N = 3	0.86	0.73	0.51	0.34	0.22	0.13	.0064	0.027	0.008	0.001

Following identification of the MTD using 3 or 6 patients, an additional 9 patients will be enrolled to further assess safety. If MTD was determined using 3 patients, then a total of 12 patients will be enrolled at the MTD, whereas, if the MTD was determined using 6 patients, then 15 patients will be enrolled at the MTD. The MTD will be exceeded if more than 33% of patients enrolled at the MTD experience DLT. In the case of 12 patients treated at the MTD, the chance of seeing no DLT, given a true underlying DLT rate of 30% is 1.4%. In the case that 15 patients are treated at the MTD, the chance of seeing one or fewer DLT, given a true underlying DLT rate of 30%, is 3%.

Expanded Cohort 2:

The probability of failing to observe toxicity in a sample size of 3 patients given various true underlying toxicity rates is shown in the Table16. Following identification of the MTD using 3 patients, at least 3 additional patients will be enrolled to further assess safety.

10.2. Phase 2

10.2.1. Sample Size Justification

The study population for safety will include all patients receiving at least a portion of one dose of TRC105. The study population for efficacy will include all randomized patients (intention to treat). The primary endpoint is PFS and the primary analysis will compare the TRC105 and control groups using a one-sided, stratified (by performance status) log-rank test at the $\alpha=0.10$ level of significance. The primary analyses of efficacy endpoints dependent on disease assessments (PFS, ORR and DR) will be performed in the intent-to-treat (ITT) population based on results of the central review of disease response and progression. Supportive analyses will be performed based on investigator assessments of disease response and progression. Pre-planned assessments of the primary endpoint will additionally be done based on number of prior therapies (one, two or three) and other known prognostic factors.

A hazard ratio of 0.67 is considered to be clinically relevant. Based on 1:1 randomization and the use of a one-sided log-rank test at the $\alpha=0.10$ level of significance, 115 events are required in order to have 80% power to detect a hazard ratio of 0.67. The expected PFS of patients treated with axitinib who have progressed following first line treatment with a VEGFR TKI is 4.8 months. Based on a planned accrual period of 12 months, and a minimum follow-up period of 4.3 months, approximately 150 patients will be required.

An interim analysis for futility will be conducted by the DMC when 55 events have occurred. At the interim analysis, the conditional power based on the observed hazard ratio will be estimated. If the conditional power is less than 25%, the DMC may recommend to the sponsor that the study be terminated for futility. However, this interim analysis will not consider the possibility of early termination on the basis of superior efficacy.

10.3. Definition of Analyzed Study Populations

The following study populations will be considered when reporting study results:

- For Phase 1b, the study population for safety includes all patients receiving at least a portion of 1 dose of TRC105.
- For Phase 1b, patients with treatment-related DLT and those without DLT who received less than the prescribed dose of TRC105 or axitinib due to documented toxicity in Cycle 1 will be considered evaluable for dose-escalation purposes. Only those patients who are deemed "ineligible" or who receive no therapy will be eliminated from the analysis. Ineligible patients who receive therapy will not be included in the assessment of efficacy endpoints, but their data will be included in the assessment of all adverse event reporting

-
- For Phase 1b, the study population for efficacy will include all safety population patients who have baseline and follow-up tumor measurements as required for assessment by RECIST 1.1.
 - For Phase 2 the study population for safety includes all patients receiving at least a portion of 1 dose of TRC105.
 - For Phase 2, the study population for efficacy will include all randomized patients (intention to treat).

10.4. Data Analysis

Descriptive statistics (such as means, medians, standard deviations and ranges for continuous data and percentages for categorical data) will be used to summarize patient characteristics, treatment administration/compliance, immunogenicity (APA), efficacy, pharmacokinetic parameters (phase 1b), protein biomarkers, and archival tumor tissue. Data will also be displayed graphically, where appropriate.

10.5. Analysis of Primary and Secondary Objectives

10.5.1. Phase 1b

For each cohort, DLTs will be summarized by category (hematologic and non-hematologic) and by MedDRA preferred term.

All AEs with an onset after initiation of treatment will be considered as treatment-emergent AEs. A preexisting condition that worsens during the treatment period will also be considered as a treatment emergent AE. All AEs will be coded by system organ class (SOC) and preferred term using NCI CTCAE (MedDRA) version 4.0.

The number and percentage of patients with the following types of treatment-emergent AEs will be summarized: common and serious AEs, AEs related to study medication, AEs resulting in study discontinuation, and clinically significant laboratory abnormalities. Non-treatment-emergent serious AEs will be described separately. Deaths will be reported with demographic information.

10.5.2. Phase 2

The primary endpoint for efficacy will be PFS, defined as time from randomization to either first disease progression (per independent radiology review of images by RECIST) or death from any cause. PFS will be censored on the day following the date of the last tumor assessment documenting absence of progressive disease for patients who do not have objective tumor progression and are still on study at the time of analysis, are given antitumor treatment other than the study treatment, are removed from study follow-up prior to documentation of objective tumor progression, died of non-cancer causes including death due to an unknown cause in the absence of documented disease progression.

The PFS distributions in the two arms will be summarized using the Kaplan-Meier method. The distributions will be compared using a stratified (by performance status) log-rank test at the one-sided $\alpha=0.10$ level of significance.

Additional exploratory analyses of PFS will be conducted in subgroups defined based on number of prior therapies (one, two or three). The same methods as for the primary analysis (Kaplan-Meier survival estimation, log rank tests) will be used. The effects of these covariates may also be assessed using Cox proportional hazards regression models.

The best response (CR, PR, SD or PD according to RECIST 1.1 and according to Choi criteria) for each patient with measurable disease who received at least one dose of study drug will be listed by cohort and response rate (CR or PR) between the two arms will be compared by Chi-square test or Fisher exact test. Stable disease will be defined as lack of tumor progression lasting for 2 cycles or longer. Additional analysis will be conducted based on duration of response, defined from the time to first response (CR or PR) to disease progression and will be compared between arms using Kaplan Meier methods. Other secondary analysis would include disease stability rate (DSR) defined as the percent of subjects in ITT population with CR, PR and SD at 12 weeks, and will be compared by Chi-square test or Fisher exact test.

All AEs with an onset after initiation of treatment will be considered as treatment-emergent AEs. A preexisting condition that worsens during the treatment period will also be considered as a treatment emergent AE. All AEs will be coded by system organ class (SOC) and preferred term using NCI CTCAE (MedDRA) version 4.0.

The number and percentage of patients with the following types of treatment-emergent AEs will be summarized for each study arm: common and serious AEs, AEs related to study medication, AEs resulting in study discontinuation, and clinically significant laboratory abnormalities. Laboratory data will be summarized for baseline, treatment visits and change from baseline as appropriate for each arm. Non-treatment-emergent serious AEs will be described separately. Deaths will be reported with demographic information. Comparison of categorical values will be made by Chi-square or Fisher exact test and of continuous variables will be made by Student t test.

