11.1 Primary Endpoint

The primary endpoint for efficacy in Phase 2 will be PFS. For Phase 2, PFS is defined as time from randomization to either first disease progression (by RECIST 1.1) or death from any cause. For Phase 1, PFS is defined from the date of consent to either first disease progression by RECIST 1.1 or death from any cause.

For the purpose of analysis for patients who are alive at the time of analysis and have not had disease progression, the following rules will apply:

- (1) The patient will be censored on the date of the last tumor assessment documenting absence of progressive disease
- (2) If the patient was given antitumor treatment other than study drug treatment, the patient will be censored as of the date of the last tumor assessment prior to initiating that antitumor therapy
- (3) If the patient was removed from study for toxicity or other reason, the patient will be censored as of the date of the last tumor assessment on study.

With regard to missed tumor assessments:

- (1) In the event of one missed tumor assessment followed by a subsequent assessment of progressive disease (PD), the subsequent PD assessment qualifies as objective tumor progression.
- (2) In the event of more than one consecutive missing tumor assessment followed by a subsequent assessment of PD, the patient will be censored at the last adequate tumor assessment. If individual scans are performed on different dates, but contribute to the same overall assessment, the date of the earliest scan will be used.

The PFS distributions in the two arms will be summarized using the Kaplan-Meier method. The distributions will be compared using a stratified (by the randomization stratification factor) log-rank test at the one-sided $\alpha=0.10$ level of significance.

Additional exploratory analyses of PFS will be conducted in subgroups defined based on number of prior therapies (one, two or three), ECOG performance status, and the biomarkers TGF- β receptor III and osteopontin. The same methods are for the primary analysis (Kaplan-Meier

survival estimation, log rank tests) will be used. The effects of these covariates may also be assessed using Cox proportional hazards regression models.

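### Protocol 10.5.2 counts every death as a PFS event and then censors deaths from non-cancer or unknown causes; SAP 11.1 has no such exception, and the two need reconciling

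*Protocol*

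**What the plan says.** Protocol 10.5.2 (Phase 2) defines primary PFS as "time from randomization to either first disease progression (per independent radiology review of images by RECIST) or death from any cause". The next sentence gives the censoring rule: "PFS will be censored on the day following the date of the last tumor assessment documenting absence of progressive disease". It applies this to patients without objective progression in four situations. They are still on study at the analysis, have been given other antitumor treatment, have been removed from follow-up before progression was documented, or "died of non-cancer causes including death due to an unknown cause in the absence of documented disease progression".

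SAP 11.1 uses the same event, "time from randomization to either first disease progression (by RECIST 1.1) or death from any cause". Its three general censoring rules are introduced with a limit on scope: "for patients who are alive at the time of analysis and have not had disease progression, the following rules will apply". Under the first rule, "The patient will be censored on the date of the last tumor assessment documenting absence of progressive disease". The second covers other antitumor therapy ("If the patient was given antitumor treatment other than study drug treatment, the patient will be censored", at the last assessment before that therapy) and the third covers removal from study. A separate rule concerns "more than one consecutive missing tumor assessment followed by a subsequent assessment of PD, the patient will be censored" at the last adequate assessment. None of these rules mentions cause of death.

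SAP 15, the section for changes from the protocol-specified analysis, lists no change. It says the plan is based on the 22Feb2016 protocol.

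**The concern.** An analyst could cite either document for the primary endpoint and classify the same death differently. If the protocol clause were followed, whether a death counts would depend on attributing its cause, in a trial that Protocol 2.3.3 describes as open label. Unknown-cause deaths without documented progression would be censored by default. A fatal toxicity without progression would leave the primary test and be censored at about the last scan, although it would still appear in the safety tables under SAP 12.2. The choice also decides which deaths count towards the 55-event futility look and the 115-event target. If the rule were chosen after outcome data had accrued, the event definition would be a post hoc decision.

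**Working it through.** **Text, side by side**

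| Patient without documented progression | Protocol 10.5.2 | SAP 11.1 |
|---|---|---|
| Dies of a non-cancer or unknown cause | Event by the definition; censored by the next sentence | Event |
| Given other antitumor treatment, then dies | Event by the definition; the clause, not limited to living patients, can censor | Event (rule 2 covers living patients only) |
| Removed from follow-up, then dies | As in the row above | Event (rule 3 covers living patients only) |
| Alive at analysis | Censored the day after the last progression-free scan | Censored on the date of that scan |

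The first row is the contradiction. The next two show that deleting the cause-of-death clause alone would leave other routes by which Protocol 10.5.2 could censor a death. The one-day difference in the last row is numerically negligible.

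**The plan's event count.** Inputs from Protocol 10.2.1 and SAP 4.2: HR 0.67, one-sided alpha 0.10 (z = 1.2816), power 80% (z = 0.8416), 1:1 allocation, 115 events.
- Schoenfeld: 4 × (1.2816 + 0.8416)² / (ln 0.67)² = 112.4, so 113.
- Freedman: (1.2816 + 0.8416)² × (1.67/0.33)² = 115.4, so 116.
- Both are close to 115, and neither depends on which death rule applies. Power at 115 events is Φ(0.4005 × √115 / 2 − 1.2816) = 80.7%.

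The documents give no rate for these deaths, so everything below is illustration.

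**Balanced deaths, power.** Suppose k deaths are censored and not replaced, split evenly, with HR 0.67 on the remaining events. Power = Φ(0.4005 × √(115 − k) / 2 − 1.2816):
- k = 3: 79.9%
- k = 6: 79.1%
- k = 12: 77.4%

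**Balanced deaths, type I error.** This was simulated with 75 patients per arm, exponential PFS with median 4.8 months in both arms, 12-month uniform accrual, no dropout, an unstratified log-rank test, data cut at the 115th all-cause event, and censored deaths backdated to the last 56-day scan plus one day (20,000 trials per setting). With 0, 2.5, 5 and 10% of events censored as such deaths, one-sided rejection was 9.9, 10.3, 10.1 and 9.9% (standard error 0.2 points). There is no inflation.

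**Imbalance.** Hold the all-cause HR at 1 with 57.5 events per arm, and censor k1 deaths on TRC105 and k0 on axitinib. Apparent HR = (1 − k1/57.5) / (1 − k0/57.5). Rejection = Φ(−ln HR × √(115 − k1 − k0) / 2 − 1.2816):
- 2 vs 1: HR 0.982, rejection 11.8%
- 2 vs 0: HR 0.965, rejection 13.7%
- 0 vs 2: HR 1.036, rejection 7.1%

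The reference value is 10%. These rates are conditional on an assumed split and are not operating characteristics of the design.

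**Effect on the estimate.** Assume such deaths make up 5% of the control PFS hazard, the HR on the rest is 0.67, and their hazard on the combination is m times control. Any-cause HR = 0.95 × 0.67 + 0.05 × m, which is 0.69, 0.74 or 0.79 for m = 1, 2 or 3. The protocol clause would give 0.67 in each case.

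**The case against.** The strongest reply is that SAP 11.1, the more detailed analysis document, already settles the matter: as written it censors no death for its cause. That stands, and it limits the harm to the case where the protocol clause is followed instead. It does not remove the point, because nothing in the supplied text gives the SAP precedence and the protocol sentence contradicts its own definition.

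It is also fair to say that the expected effect may be small. The safety background offers little support for a high rate: no grade 5 related event appears in the 50-patient monotherapy table, and none was reported in the 38-patient bevacizumab study described in Protocol 2.3.2.1. Protocol 2.3.6.1 does report one fatal intracranial hemorrhage, in a glioblastoma patient given TRC105 with bevacizumab. The two study reports concern related events only, so they set no ceiling on non-cancer or unknown-cause deaths here.

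A reader might go further in three ways that the documents do not support:
- **That the primary result will be biased towards TRC105.** No death rate or imbalance is given, the direction depends on which arm has more such deaths, and balanced deaths leave type I error unchanged.
- **That the SAP is silent on deaths after new therapy or missed scans.** The alive-only scope covers the new-therapy rule, and the missed-scan rule concerns a later PD, so such deaths fall under the any-cause definition.
- **That an unlogged departure from the governing protocol is proven.** The supplied protocol's date is not visible and cannot be confirmed as 22Feb2016.

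**Conclusion.** The primary endpoint rule in Protocol 10.5.2 is wrong as written, and this holds whichever protocol version was supplied. The mismatch with SAP 11.1 and the missing SAP 15 entry hold if the supplied protocol is the version the SAP cites. This is a needed reconciliation of the primary-endpoint definition, not evidence that the result would be biased.

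The size cannot be determined from the documents. With an even split, 3 to 12 uncounted deaths cost about 0.8 to 3.3 points of power (80.7 − 79.9 and 80.7 − 77.4). Waiting for 115 counted events would avoid that loss, but SAP 4.2 allows the final analysis before 115. An imbalance of one or two deaths moves the conditional one-sided rejection rate from 10% to between 7.1% and 13.7% in the cases shown. These figures rest on proportional hazards and on assumed numbers of deaths.

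**What to change.** - **Protocol 10.5.2:** replace the censoring sentence with the general rules of SAP 11.1. The non-cancer and unknown-cause death clause goes. The remaining clauses (still on study, other antitumor treatment, removed from follow-up) apply only to patients alive without progression at the analysis. This also aligns the censoring date.
- **Both documents:** state that an ascertained death without prior documented progression is a PFS event on the date of death, whatever its cause, and that the 55- and 115-event counts use this definition.
- **SAP 15:** record the reconciliation and the protocol version it refers to.
- **Optional:** keep cause-specific censoring as a labelled sensitivity analysis.

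The SAP rules on missed assessments before a later PD, and on conflicts between central and investigator review, are not touched by this change.

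The cost is a few sentences of text, with no change to visits, patients or treatment. The limit is ascertainment. Scheduled follow-up ends 28 days after the last dose (Protocol Tables 9 to 11), no survival visit is planned, and under Protocol 15.1 the trial ends when all patients have completed treatment. Later deaths count only where they become known, and this edit does not improve that.
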